9.6.2 Analysis Methods for Safety Analyses

Safety and tolerability will be assessed by clinical review of all relevant parameters including AEs, laboratory tests, body weight, and vital signs.

Adverse Events

AEs will be coded using the standard MedDRA and grouped according to SOC.

The analysis of safety results will follow a tiered approach (Table 7). The tiers differ with respect to the analyses that will be performed.

Tier 1 Events

The safety profile of MK-3655 is not understood sufficiently to prespecify any Tier 1 events.

Tier 2 Events

Tier 2 parameters will be assessed via point estimates with 95% CIs provided for between-treatment differences in the proportion of participants with events.

Membership in Tier 2 requires that at least 4 participants in any treatment group exhibit the event; all other AEs and PDLCs will belong to Tier 3. The threshold of at least 4 events was chosen because the 95% CI for the between-group difference in percent incidence will always include zero when the treatment groups each have fewer than 4 events and thus would add little to the interpretation of potentially meaningful differences. Because many 95% CIs may be provided without adjustment for multiplicity, the CIs should be regarded as a helpful

descriptive measure to be used in review, not a formal method for assessing the statistical significance of the between-group differences in AEs and PDLs.

In addition, summary measures of AEs consisting of the percentage of participants with any AE, with a drug-related AE, with an SAE, with an AE which is both drug-related and serious, who discontinued due to an AE, and who died will be considered Tier 2 endpoints.

The 95% CIs will be provided for between-treatment differences in the percentage of participants with each Tier 2 event; these analyses will be performed using the M&N method [Miettinen, O. and Nurminen, M. 1985].

Weight change from baseline will also be considered a Tier 2 endpoint. This analysis will be performed using a cLDA model as described for LFC in Section 9.6.1.2.

Tier 3 Events

Safety endpoints that are not Tier 2 events will be considered Tier 3 events. Only point estimates by treatment group will be provided for Tier 3 safety parameters.

Continuous Safety Measures

For continuous measures such as changes from baseline in laboratory and vital signs parameters, summary statistics for baseline, on treatment, and change from baseline values will be provided by treatment group.

Adjudicated Adverse Experiences

For AEs prespecified for adjudication (CV and malignancy), results of adjudication will be summarized. Further details may be provided in the sSAP.

Safety Topics of Special Interest

Safety topics of special interest include suicidal ideation and behavior evaluated by C-SSRS, depression severity evaluated by PHQ-9, and AEs reflecting abuse potential. The AEs reflecting abuse potential will be analyzed as Tier 2 or Tier 3 analogously to AEs. Further details will be provided in the sSAP.

Table 7 Analysis Strategy for Safety Parameters

Safety Tier	Safety Endpoint	p-Value for Treatment Comparison	95% CI for Treatment Comparison	Descriptive Statistics
Tier 2	Any AE	-	X	X
	Any Serious AE	-	X	X
	Any Drug-related AE	-	X	X
	Any Serious and Drug-related AE	-	X	X
	Discontinuation Due to AE	-	X	X
	Death	-	X	X
	Specific AEs, SOCs, or PDLCs (Incidence \geq 4 Participants in one of the Treatment Groups)	-	X	X
	Weight Change From Baseline	-	X	X
	AEs Reflecting Abuse Potential (Incidence \geq 4 Participants in one of the Treatment Groups)	-	X	X
	Tier 3	Specific AEs, SOCs, or PDLCs (Incidence $<$ 4 Participants in all the Treatment Groups)	-	-
Change From Baseline Results (Laboratory Tests, ECGs, Vital Signs)		-	-	X
ADA		-	-	X
Adjudicated Events (CV and malignancy)		-	-	X
AEs Reflecting Abuse Potential (Incidence $<$ 4 Participants in one of the Treatment Groups)		-	-	X
C-SSRS and PHQ-9		-	-	X

ADA=anti-drug antibodies; AE=adverse event; CI=confidence interval; C-SSRS=Columbia-Suicide Severity Rating Scale; CV=cardiovascular; ECG=electrocardiogram; PDLC=predefined limit of change; PHQ-9=Patient Health Questionnaire – 9; SOC=system organ class; X=results will be provided.

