Lifestyle modification directed at weight loss and exercise remain the most recommended treatment for NAFLD; however, even in well-organized settings, only a minority of patients achieve and sustain weight loss. Presently, there are no agency approved medications for the treatment of NASH. According to evidence-based practice guidelines, pioglitazone and high dose vitamin E (800 IU/day) are now recommended as pharmacotherapies for biopsy-proven NASH patients with and without diabetes, respectively [Sumida, Y. 2018]. However, neither pioglitazone nor vitamin E have demonstrated in the NASH population a robust histological efficacy, been studied long-term to assess impact on liver-related outcomes or have fully characterized safety. The absence of well-characterized, safe, and highly effective NASH treatments is a significant unmet medical need recognized by both medical societies and regulatory agencies [Friedman, S. L., et al 2018] [Food and Drug Administration 2018] [Chalasani, N., et al 2018].

The focus of this study is to evaluate MK-3655, a humanized mAb that selectively activates the FGFR1c/KLB receptor complex that mediates most or all the metabolic benefits of FGF21 and its pharmacologic analogs including insulin sensitization, lipid profile improvements, and liver fat reduction [Owen, B. M., et al 2015] [Sanyal, A., et al 2018]. FGFR1c/KLB is also considered the principal target mediating the robust anti-steatotic effect reported for a FGF19 analog [Owen, B. M., et al 2015] [Harrison, S. A., et al 2018]. Unlike FGF21 and FGF19 analogs, MK-3655 selectively activates only FGFR1c/KLB, which may confer an optimal therapeutic profile through avoidance of unfavorable effects potentially mediated by activation of other FGFR/KLB complexes. FGF21-mediated activation of FGFR2/KLB and FGFR3/KLB may potentially contribute to unfavorable effects which have been associated with FGF21s including effects on the hypothalamic-pituitary axis, bone, heart rate, blood pressure, glucocorticoids, and female reproductive function [Wei, W., et al 2012] [Talukdar, S., et al 2016] [Kim, A. M., et al 2017] [Owen, B. M., et al 2015] [Owen, B. M., et al 2013] [Singhal, G., et al 2016]. FGFR4/KLB-mediated modulation of bile acid metabolism is presumed to be responsible for the substantial LDL-C elevation seen with administration of an FGF19 analog [Harrison, S. A., et al 2018].

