Weight gain was also observed among participants randomized to multiple doses of MK-3655 in Study P002 and Study P003. In these studies, the final dose of MK-3655 was administered on Day 50 and weight gain continued for several weeks after the final dose up to a maximum placebo adjusted increase of 5% to 6% from baseline. The trajectory and magnitude following 150 mg Q1W dosing was similar to that following 120 mg Q4W or 240 mg Q4W dosing, suggesting that dosing regimens \geq 120 mg Q4W do not result in greater weight gain. Clinical assessments, including physical examination and laboratory values, do not support fluid retention as a major contributor to weight gain. Exploratory analyses in the MAD module of Study P004, in Study P002 and in Study P003 using DXA measurements suggest the observed increase in body weight is due to increased accumulation of adipose tissue.

In both the P002 study and P003 study, greater increases in mean pulse and ventricular rate change from baseline were seen in the MK-3655 group than in the placebo group, but the between-group differences were typically small in magnitude and of uncertain clinical significance. Additionally, no meaningful differences in systolic or diastolic blood pressure were observed between the MK-3655 group and the placebo in either study.

Based on the clinical program to date, which has explored exposures above those planned for this study, no signals have been identified that would preclude further clinical development.

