4.2.1.3 Safety Endpoints

The safety data for MK-3655 to date has been described in detail in Section 2.2.2 and in the IB.

In support of the safety objective to evaluate the safety and tolerability profile of MK-3655, the safety and tolerability endpoints will be assessed by clinical evaluation of AEs (including adjudication of malignancies and CV events) and inspection of other study parameters including vital signs (ie, heart rate, blood pressure, temperature), body weight, physical examination, standard laboratory safety tests, 12-lead ECGs, ketone levels, BMD by DXA, and evaluation of biomarkers of bone formation (P1NP) and resorption (CTX) will be performed. Additional class-related hypothalamic-pituitary function safety endpoints will be assessed including bedtime salivary cortisol, ACTH, TSH, FT4, and IGF-1.

All procedures will be conducted at the time points specified in the SoA. AEs will be graded and recorded throughout the study and during the follow-up period according to NCI CTCAE, Version 5.0 (see Section 10.14). **Note:** For AEs that are an exception to the NCI CTCAE grading, see Section 7.1.

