Published nonclinical data suggest potential for a weight-independent, mechanism-based effect of FGF21 on bone [Wei, W., et al 2012] [Owen, B. M., et al 2015]. Administration of one FGF21 analog in humans resulted in bone biomarker changes consistent with net bone loss, though there was potentially confounding concurrent weight loss [Talukdar, S., et al 2016]. Notably, there was no evident impact of MK-3655 on biomarkers of bone formation (P1NP) or resorption (CTX) or on DXA-assessed BMD over 12 weeks of dosing in the MAD part of MK-3655 P004 study (NGM 15-0201). There was also no evident impact of MK-3655 on P1NP or CTX over 8 weeks of dosing in MK-3655 P002 in which exposures over the last 4 weeks of dosing (AUC_{D29-57} : 989 day* $\mu\text{g}/\text{mL}$) were approximately 2-fold greater than those predicted for the top (300 mg Q4W) dose arm in this study and approached the exposures at which decreased bone mineral content was observed in female NHPs ($\geq AUC_{D0-28}$: 971 day* $\mu\text{g}/\text{mL}$). The observed trend to reversibility of the bone mineral content effect in chronic toxicology provides additional reassurance regarding safety for study participants.

Menstrual cycle prolongation, which was previously observed in the chronic toxicity study, was not recapitulated at comparable MK-3655 exposures in a 4-month repeat-dose study dedicated to assessing menstrual cyclicity in cynomolgus monkeys. MK-3655 treatment resulted in substantial body weight loss but did not cause menstrual cycle changes in a large cohort of regularly cycling NHP evaluated in this study. At the NOEL of the NHP menstrual cyclicity study, MK-3655 exposure was 2-fold higher than the projected clinical exposure at 300 mg Q4W. Based on these data, menstrual cycle changes in the chronic toxicity study are attributed to normal variability in length of menstrual cycles in NHP, changes in social housing conditions, and/or stress/poor body condition resulting from body weight loss. Therefore, the totality of the MK-3655 nonclinical data indicate that MK-3655 does not cause menstrual cycle changes in cynomolgus monkeys. Further, based on the totality of the nonclinical data, there is no evidence that MK-3655 will impact fertility in female or male participants (see IB).

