The accrued bone biomarker and DXA data summarized above suggest low risk for MK-3655 to have deleterious bone effects. To expand this characterization, bone biomarkers (P1NP and CTX) and BMD (DXA) will be assessed in this study. To minimize the potential for confounding these assessments, participants will be excluded from study participation if at Visit 1/Screening they have a known history of osteoporosis or other indication for treatment with specified bone-active agents (see Section 5.2). Participants **will not** be excluded if an indication for treatment with the bone-active pharmacological classes of agents listed in Section 5.2 is identified after Visit 1/Screening. This includes any participant diagnosed with osteoporosis by DXA imaging performed during the placebo run-in. The number of such participants is expected to be small, and unlikely to undermine the study-wide characterization of bone biomarker and bone density responses. Such participants will be referred to their personal physician for management of osteoporosis.

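### No between-group estimate or 95% CI is prespecified for change in heart rate or bone mineral density, although weight change has both

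*Combined protocol and SAP*

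**What the plan says.** Section 3 sets safety and tolerability relative to placebo as a primary objective. Section 4.2.1.3 lists heart rate among the vital signs to be inspected and adds: "BMD by DXA, and evaluation of biomarkers of bone formation (P1NP) and resorption (CTX) will be performed".

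Section 9.6.2 then sorts safety measures into tiers. Tier 2 gets between-group differences with 95% CIs. For Tier 3, "Only point estimates by treatment group will be provided for Tier 3 safety parameters". Any safety endpoint that is not Tier 2 is Tier 3. Continuous measures get summary statistics by treatment group.

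- **Heart rate** is covered by the Tier 3 row of Table 7 that begins "Change From Baseline Results (Laboratory Tests, ECGs, Vital Signs". That row has a dash under both the p-value and the CI for the treatment comparison.
- **BMD** has no row in Table 7 and is not mentioned in Section 9.6.2, so it is Tier 3 by the catch-all. The DXA item among the pharmacodynamic endpoints in Section 9.4.6 is body composition, not BMD.
- **P1NP and CTX** are listed with the laboratory tests in Table 10, so they fall in the same Tier 3 row as heart rate.
- **Weight change** is placed in Tier 2 and analysed by the cLDA model of Section 9.6.1.2. It is the only continuous safety measure treated this way.

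**The concern.** The protocol gives its own reasons for interest in these two measures. Section 2.2.2.2 reports that in P002 and P003 "greater increases in mean pulse and ventricular rate change from baseline were seen in the MK-3655 group than in the placebo group", while adding that "the between-group differences were typically small in magnitude and of uncertain clinical significance". Section 2.2.1 lists possible unfavorable effects associated with FGF21s: "effects on the hypothalamic-pituitary axis, bone, heart rate, blood pressure, glucocorticoids, and female reproductive function". Section 4.3.3 says "Published nonclinical data suggest potential for a weight-independent, mechanism-based effect of FGF21 on bone", and later, of this trial: "To expand this characterization, bone biomarkers (P1NP and CTX) and BMD (DXA) will be assessed in this study".

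A set of by-arm means and SDs does not state what size of heart-rate rise or BMD loss, relative to placebo, the data are compatible with at each dose. The earlier comparisons were very small: 15 active and 5 placebo participants in P002, and 6 and 2 in the multiple-dose panel of P003. This trial plans 82 per arm over 52 weeks. If the comparison is left out of the plan, any interval reported later will have been chosen after the data were seen.

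**Working it through.** **1. Does the plan's reason for withholding CIs apply here?** Section 9.6.2 requires at least 4 participants with an event in some group, because with fewer the CI always includes zero. I checked this with the Miettinen-Nurminen score statistic at 82 per arm, z = (x1 − x2)/n ÷ √[p(1 − p)(2/n)(2n/(2n − 1))], where p = (x1 + x2)/2n.

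- 3 v 0: z = 1.74, below 1.96, so the CI includes zero.
- 4 v 0: z = 2.02, so the CI excludes zero.
- The Table 9 rows also reproduce: 7 v 1, z = 2.17; 10 v 3, z = 2.02; 15 v 6, z = 2.10.

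The threshold is right, but it concerns event counts. It gives no reason to omit a CI for a continuous measure.

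**2. Participants available.** Section 9.9.1 gives 82 per arm and about 15% drop-out by Week 52: 82 × 0.85 = 69.7, about 70. For heart rate I take 60 to 70. For BMD I assume 50 to 65 with paired scans. That range is not in the documents, but Section 8.3.8 makes DXA conditional on willingness, ability and country law, allows no repeat after failed quality control, and requires a valid baseline scan.

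**3. Precision of the omitted intervals.** Unadjusted 95% half-width = 1.96 × SD × √(2/n). In SD units this is 0.31 at 82 per arm, 0.33 at 70 and 0.39 at 50. The documents give no SD for either change, so the SDs below are assumptions.

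| Measure | Assumed SD | n per arm | Half-width |
|---|---|---|---|
| Heart rate | 8 bpm | 70 | 1.96 × 8 × √(2/70) = 2.7 bpm |
| Heart rate | 10 bpm | 60 | 1.96 × 10 × √(2/60) = 3.6 bpm |
| BMD % change | 2.5 points | 65 | 1.96 × 2.5 × √(2/65) = 0.9 points |
| BMD % change | 4 points | 50 | 1.96 × 4 × √(2/50) = 1.6 points |

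Baseline adjustment would narrow these.

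**4. Against Phase 1.** With 15 v 5 (P002) the same formula gives 1.96 × √(1/15 + 1/5) = 1.01 SD. At 70 per arm it is 0.33 SD, about three times tighter.

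**5. Data already collected.** Section 8.3.7 takes heart rate in triplicate at every site visit except Visits 2 and 3. The Schedule of Activities has DXA at Visit 4 and Week 52.

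**The case against.** The case for leaving the plan alone has real substance.

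- **The prior signals are weak.** The heart-rate differences were typically small, and exposures in P002 and P003 were about 2.1-fold and 2.6-fold those predicted for 300 mg Q4W. Section 2.2.1 links the possible FGF21 effects to FGFR2/KLB and FGFR3/KLB, which MK-3655 is said not to activate. P004 showed no evident effect on BMD, P1NP or CTX over 12 weeks. This stands. It lowers the urgency but does not supply the 52-week comparison.
- **A crude comparison is possible.** By-group means give a difference, and if n and SD are tabulated, an unadjusted CI. This stands, so a reader should not infer that the trial yields no comparison at all. What is missing is a prespecified interval adjusted for the stratification factors.
- **Other safeguards exist.** Clinically significant vital-sign findings become AEs, and specific AEs reach Tier 2 at 4 participants in a group. Serious CV events are adjudicated, and the eDMC reviews safety. None of these estimates a mean shift.
- **The sSAP may add it.** It may, but the sSAP deferrals in Section 9.6.2 are for adjudicated events and topics of special interest, not vital signs or BMD.
- **The choice is a judgement.** The named primary safety endpoints are AEs and discontinuations due to AEs, and Section 9.6.2 calls even Tier 2 CIs descriptive. This stands, and it limits the weight of the point.

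Two stronger readings are tempting. A reader might infer that heart rate rose in every multiple-dose Phase 1 study. In fact P004 and P006 also had multiple dosing, and the rise is reported only for P002 and P003. A reader might also infer that BMD monitoring is what justifies exceeding the animal NOAEL. Section 4.3.3 refers to protocol mitigations in general but in that argument names only body-weight assessment. Its bone argument rests on accrued Phase 1 data and on a trend to reversibility in toxicology.

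**Conclusion.** The gap is real but modest. Section 9.6.2 and Table 7 prespecify no between-group estimate or CI for heart-rate or BMD change, although the safety objective is comparative and the protocol itself gives reasons to look at both. The only reason stated for withholding intervals applies to rare events. On the assumed SDs and sample sizes, the omitted intervals would be about ±2.7 to 3.6 bpm and ±0.9 to 1.6 percentage points, much tighter than Phase 1 allowed. No hypothesis test, error rate or sample size is affected. This is a cheap improvement, not a defect that threatens the trial's conclusions.

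**What to change.** Add Tier 2 rows to Table 7 for heart-rate change from baseline and for percent change in lumbar-spine and hip BMD at Week 52. P1NP and CTX are optional. Report MK-3655-minus-placebo differences with 95% CIs for each dose from the cLDA model already planned for weight, without p-values and labelled descriptive.

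For BMD, the text should also:

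- define the analysis set as participants with a valid baseline DXA;
- state how scans from discontinuation visits (possible from 24 weeks) are handled, since LFC and histology have a nearest-to-nominal-visit rule and BMD has none;
- say how percent change is obtained from a model whose response includes the baseline value, for example by modelling log BMD and back-transforming;
- say whether participants who start bone-active agents after screening are included as observed.

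The cost is a few more tables, the BMD decisions above, and more CIs unadjusted for multiplicity, which Section 9.6.2 already describes as a descriptive aid. No additional participants, visits or procedures are needed.

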9.6.3 Summaries of Demographic and Baseline Characteristics

The comparability of the treatment groups for each relevant demographic and baseline characteristic will be assessed using tables and/or graphs. No statistical hypothesis tests will be performed on these characteristics. The number and percentage of participants screened and randomized and the primary reasons for screening failure and discontinuation will be displayed. Demographic variables (eg, age), baseline characteristics, primary and secondary diagnoses, and prior and concomitant therapies will be summarized by treatment either by descriptive statistics or categorical tables.

9.7 Interim Analyses

A single IA is planned for both administrative purposes and to assess futility. The IA is planned to be performed once \geq 25 participants per group have had LFC measured at the Week 24 post-randomization assessment. Key endpoints to be evaluated include LFC (efficacy), body weight, AEs, and laboratory PDLC.

The IA will be conducted by limited Sponsor personnel not otherwise involved in study conduct, who will be unblinded to treatment information. Results of the IA will be reviewed by an eDMC with recommendations provided to an internal EOC.

The administrative purpose addressed by the IA is to enable the EOC to assess whether the interim results are favorable enough to merit initiation of additional programmatic activities. The EOC will review unblinded interim results on a recommendation by the eDMC. Criteria for this recommendation will be provided in the eDMC charter. If the EOC considers that interim data warrant administrative action regarding other aspects of the development program, the unblinded interim data may be reviewed by additional individuals with responsibility for programmatic oversight. Individuals directly involved in study conduct will not have access to unblinded interim results.

The study may stop for futility if the posterior probability is <5% that the true mean difference (MK-3655 minus placebo) in percent reduction from baseline in LFC is $\geq 40\%$ for all MK-3655 treatment groups. If this non-binding futility criterion is met, the EOC, and possibly additional individuals with responsibility for programmatic oversight, will review unblinded interim results on a recommendation by the eDMC. The study will be stopped for futility if the EOC considers this to be warranted.

The study will neither stop nor be modified unless the futility criterion is met as defined for all MK-3655 groups. There is a 5.0% (<0.1%) chance of observing a posterior probability <5% for a given treatment group if the true mean difference is 40% (50%). There is 0.01% chance that all MK-3655 doses meet the futility criterion if the true mean difference (MK-3655 minus placebo) is 40% for all dose levels. There is a >99% chance that the criterion for stopping for futility will be met if MK-3655 doses are not different from placebo. The posterior probabilities that the true mean difference (MK-3655 minus placebo) in percent relative reduction from baseline in LFC is $\geq 40\%$ for a range of observed differences in percent reduction from baseline in LFC are presented in Table 8. An observed mean difference <30% for any given MK-3655 dose level would have a posterior probability <5%. All calculations assume a common standard deviation of 20% as well as a normal distribution for the percent relative reduction in LFC.

Table 8 Posterior Probabilities for Observed Differences in % Relative Reduction in LFC

Observed Difference (MK-3655 Minus Placebo) in % Relative Reduction in LFC	Posterior Probability^a
30%	4.2%
35%	19.1%
38%	36.3%
40%	50.0%

LFC=liver fat content.
^a Posterior probability that the true mean difference (MK-3655 minus placebo) in percent relative reduction from baseline in LFC is $\geq 40\%$.

Study enrollment is likely to be ongoing at the time of the IA for futility. Blinding to intervention assignment will be maintained at all investigational sites. The results of the IA will not be shared with the investigators before the completion of the study. Participant-level

unblinding will be restricted to an internal unblinded statistician and scientific programmer performing the IA, who will have no other responsibilities associated with the study.

The eDMC charter will be referenced in the CSR. Before final study unblinding, individuals who have been unblinded at any level will not be involved in any discussions regarding modifications to the protocol, statistical methods, identification of protocol deviations, or data validation efforts after the IA.

The eDMC will also perform rigorous reviews of safety information obtained during the clinical study. Details about the frequency and content of these reviews will be provided in the eDMC charter.

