9.1 Statistical Analysis Plan Summary

Key elements of the SAP are summarized here. The comprehensive plan is provided in Sections 9.2 through 9.12.

Study Design Overview	A Phase 2b Randomized, Double-Blind, Placebo-Controlled Study to Evaluate the Efficacy and Safety of MK-3655 in Individuals With Pre-cirrhotic Nonalcoholic Steatohepatitis
Treatment Assignment	Participants (82 per group) will be randomized in a 1:1:1:1 ratio among 4 treatment groups: (1) MK-3655 50 mg Q4W, (2) MK-3655 100 mg Q4W, (3) MK-3655 300 mg Q4W, and (4) matching placebo.
Primary Analysis Populations	Efficacy: FAS Safety: APaT
Primary Endpoint	
 NASH resolution without worsening in fibrosis by histology (evaluated by BICR) after 52 weeks
Key Secondary Endpoints	
 Percent relative reduction in LFC based on MRI-PDFF (evaluated by BICR) after 24 weeks ≥1 stage improvement in fibrosis without worsening of steatohepatitis by histology (evaluated by BICR) after 52 weeks ≥2 point reduction in NAS with ≥1 point reduction in inflammation or ballooning without worsening of fibrosis by histology (evaluated by BICR) after 52 weeks
Statistical Methods for Key Efficacy Analyses	
Primary:
 
 The differences in proportions and the associated 95% CI and p-values will be provided (MK-3655 minus placebo; 3 pair-wise comparisons) based on the stratified M&N method [Mehrotra, D. V. 2000]. 
Key Secondary:
 
 For LFC, the differences in means and the associated 95% CIs and p-values will be provided (MK-3655 minus placebo; 3 pair-wise comparisons) based on a cLDA model. Other key secondary endpoints will follow methods for the primary efficacy endpoint.
Statistical Methods for Key Safety Analyses	For analyses in which 95% CIs will be provided for between-treatment differences (MK-3655 minus placebo) in the percentage of participants with events, these analyses will be performed using the M&N method [Miettinen, O. and Nurminen, M. 1985].

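### Section 9.7 gives a 0.01% chance that all three doses meet the futility criterion at a true 40% difference; with one shared placebo group it is about 0.5%

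*Combined protocol and SAP*

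**What the plan says.** Section 9.7 plans one interim analysis, once at least 25 participants per group have a Week 24 LFC measurement. The criterion is set per dose: "The study may stop for futility if the posterior probability is <5% that the true mean difference (MK-3655 minus placebo") in percent LFC reduction is at least 40%. It must hold for every active group: "The study will neither stop nor be modified unless the futility criterion is met as defined for all MK-3655 groups".

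The section then gives these operating characteristics:

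- For a single dose, the chance of meeting the criterion is 5.0% if the true difference is 40%, and below 0.1% if it is 50%.
- For all doses together, with a true difference of 40% at each: "There is 0.01% chance that all MK-3655 doses meet the futility criterion".
- If no dose differs from placebo, the chance of meeting the criterion is above 99%.

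The stated basis is: "All calculations assume a common standard deviation of 20% as well as a normal distribution for the percent relative reduction in LFC". The section does not say how the joint figure was obtained and does not mention correlation between the comparisons.

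On the design, Section 9.1 says: "Participants (82 per group) will be randomized in a 1:1:1:1 ratio among 4 treatment groups". Three of these are MK-3655 doses and one is placebo.

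**The concern.** The criterion acts at trial level only when all three doses meet it, so the joint probability is the operating characteristic that matters. The plan gives it for just one scenario in which the doses work, namely a true 40% at every dose.

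The printed 0.01% is what results from multiplying three independent 5.0% chances. But all three differences are measured against the same placebo group. If that group happens to show a large LFC reduction, all three differences shrink together and the three doses tend to meet the criterion together. The joint probability must then exceed the independent product. Those weighing a met criterion would be relying on a figure that understates how often it occurs by chance when every dose truly reaches 40%.

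**Working it through.** **Inputs, all from the plan**

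- SD 20%, common to all groups, normal distribution (Section 9.7).
- Interim n = 25 per group, the planned minimum (Section 9.7).
- Three doses and one placebo group, randomized 1:1:1:1 (Sections 6.3.1 and 9.1).
- Chance of meeting the criterion for one dose at a true 40%: 5.0% (Section 9.7).

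**Step 1. Reproduce the figures that do not involve the joint event**

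Standard error of one difference: SE = 20 × √(2/25) = 5.657.

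Table 8, using P(t with 48 df < (observed − 40)/SE):

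| Observed difference | Recomputed | Table 8 |
|---|---|---|
| 30% | 4.2% | 4.2% |
| 35% | 19.1% | 19.1% |
| 38% | 36.3% | 36.3% |
| 40% | 50.0% | 50.0% |

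Single dose, with Φ the standard normal distribution function:

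- True 40%: Φ(−1.645) = 5.0%, as stated.
- True 50%: Φ(−1.645 − 10/5.657) = Φ(−3.413) = 0.03%, consistent with the stated figure of below 0.1%.

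So the model used here matches the plan's.

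**Step 2. Reproduce the joint figure**

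Under independence: 0.05 × 0.05 × 0.05 = 0.000125 = 0.0125%, which rounds to the printed 0.01%.

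**Step 3. Account for the shared placebo group**

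The correlation of two dose-minus-placebo differences is

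ρ = n_dose / (n_dose + n_placebo) = 25/50 = 0.5.

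Let x be the standardized deviation of the placebo mean. Given x, the three dose means are independent, so

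P(all three) = ∫ φ(x) × Φ((cut-off − 40 + x × 20/√25) / (20/√25))³ dx,

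where the cut-off is 40 − 1.645 × 5.657 = 30.70. The integral is **0.00496, that is 0.496%**.

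The trivariate normal distribution function with ρ = 0.5 agrees (0.496%). A simulation of 4,000,000 trials at n = 25 with the SD estimated from the data gave 5.02% for a single dose. For all three doses it gave 0.50% with a pairwise SD and 0.52% with the SD pooled over four groups.

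**Step 4. Sensitivity**

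- *Interim n.* At 5.0% per dose and equal groups, only ρ matters; the result is 0.496% at every n tried from 25 to 82 per group.
- *Unequal interim groups (assumed sizes, 5.0% per dose):*

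| Placebo n / dose n | ρ | Joint probability |
|---|---|---|
| 35 / 25 | 0.417 | 0.33% |
| 30 / 25 | 0.455 | 0.40% |
| 25 / 25 | 0.500 | 0.50% |
| 25 / 30 | 0.545 | 0.61% |
| 25 / 35 | 0.583 | 0.72% |

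- *Other cut-offs.* The t(48) cut-off with known SD gives 0.44%. A cut-off at an observed difference below 30% gives 0.32%, but this implies about 3.9% per dose, not the stated 5.0%.
- *Smaller correlation.* Even ρ = 0.05 gives 0.023%, which would not print as 0.01%.

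**Step 5. The no-effect statement**

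With the shared placebo group and a true difference of 0 at every dose, the joint probability exceeds 99.99%, so the plan's figure of above 99% stands.

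**The case against.** The strongest objection is to the weight of the point. Both 0.01% and 0.5% are small, and no design choice in the documents turns on which is right. The criterion is advisory: the section opens the next step with "If this non-binding futility criterion is met", sends the results through the eDMC, and adds "The study will be stopped for futility if the EOC considers this to be warranted". All of that stands. The ratio of about 40 (0.496/0.0125) should not be used to inflate the point; the absolute change is about 0.5 percentage points.

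A second objection is that the derivation is inferred. This also stands: the plan does not say it assumed independence, and the numerical match is the only evidence. But the error does not depend on that inference. No calculation tried with a single placebo group of similar size to the dose groups comes near 0.01%, and independence is not among the assumptions the section lists.

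A third caution concerns how the corrected figure is read. It applies when every dose truly reaches 40%, which is the condition in the plan's sentence. It is not a general bound on meeting the criterion when one dose is effective. Section 4.3.3 itself expects a sub-maximal LFC response at 50 mg. With the same inputs and assumed true differences for the three doses, the joint probability is 1.2% at 30/40/40, 2.9% at 30/35/40, 4.5% at 20/30/40 and 5.0% at 0/0/40. These scenarios limit the interpretation of 0.5% but do not change the correction.

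**Conclusion.** The stated 0.01% is wrong as written. Under the plan's own 5.0% per dose, normality and common SD, with one placebo group and equal group sizes, the chance that all three doses meet the criterion at a true 40% is about 0.5%. It stays between 0.33% and 0.72% over the assumed range of unequal interim groups.

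This is a misstated operating characteristic of the only futility rule, not a weakness of the rule. The consequence is modest. Because the rule is non-binding, about 0.5% is the chance of meeting the criterion in that scenario; the chance of actually stopping for futility under it can be no larger.

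**What to change.** In Section 9.7, replace 0.01% with about 0.5%, keep the condition that the true difference is 40% for all dose levels, and add a clause saying that the figure accounts for the placebo group shared by the three comparisons. "About 0.5%" is precise enough, since the interim group sizes are fixed only as a minimum.

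The cost is one figure and one clause. The rule, its threshold, the sample size and Table 8 need no change.
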